## 6. Statistical consideration

### 6.1 Power estimate

Since no prior mitoPO2 study had been performed on critically ill patients, no data was available to calculate the sample size needed for the prospective cohort study.

Therefore, we performed a pilot study with 20 subjects to assess feasibility of the mitoPO2 measurement and to calculate a standard deviation needed for the sample size calculation. The statistical significance level will be set at the 5% level. The sample size will be calculated to achieve a statistical power of 90%. We know from our pilot study performed on 20 critically ill patients that the mean mitoPO2 is 67.9 mmHg with a standard deviation of 13 mmHg. A difference in mitoPO2 of 5mmHg after red cell transfusion is deemed to be clinically relevant. Thus, the sample size calculation would subsequently be the following:

$$Z_{\alpha/2} = 1.96 \text{ (two tailed for } p = 0.05)$$

$$Z_{1-\beta} = 1.28 \text{ (for } \beta = 0.10)$$

$$\mu = 72.9 \text{ mmHg}$$

$$\mu_0 = 67.9 \text{ mmHg}$$

$$\sigma = 15 \text{ mmHg}$$

$$n = \left( \sigma \frac{Z_{\alpha/2} + Z_{1-\beta}}{\mu - \mu_0} \right)^2 = 189. \text{ With an expected 10\% drop out rate, the corrected sample size will be } 189 * 1.1 = 209 \text{ subjects.}$$

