
After inclusion of a patient meeting the eligibility criteria, each patient will be assigned an unique study number.

To determine the reliability of the mitoPO2 measurement in critically ill ICU patients with anaemia who will receive transfusion, we first assessed the variance of mitoPO2 from repeated mitoPO2 values before and after transfusion in 20 ICU patients. Next, using this variance, we estimated the number of patients needed to perform a reliable multicentre study, which we subsequently will perform.

To examine the effects of red cell transfusion and the associated change in Hb on mitoPO2, and on other physiologic measures of tissue oxygenation and oxygen balance such as DO2, VO2, ScvO2,

---

and lactate, we will compare values of all parameters before with the values after red cell transfusion. In addition we will perform similar analyses in subgroups of Hb and reason of admission to assess whether the observed effect of red cell transfusion on the parameters differs between the groups. We will also examine whether the decrease of the mitoPO2 precedes decreases of other measures of tissue oxygenation and microcirculation.

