## 5.4 Study parameters

### 5.4.1 Main study outcomes

The primary endpoint is the change of mitoPO2 before and after red cell transfusion. This will be compared to change in traditional parameters used to measure oxygenation and oxygen balance (ScvO2, SaO2, PaO2, PvO2, CI, and lactate).

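### Section 6.1: the printed formula and inputs give 95 patients, not 189; the factor 2 behind 189 is not printed, so the meaning of sigma = 15 and the power at the planned N are not fixed

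*Protocol*

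**What the plan says.** All of the following is in the Protocol.

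- Section 6.1 sets the error rates: "The statistical significance level will be set at the 5% level", with z = 1.96 ("two tailed for } p = 0.05"), and "The sample size will be calculated to achieve a statistical power of 90" percent, with z = 1.28.
- The effect to detect: "A difference in mitoPO2 of 5mmHg after red cell transfusion is deemed to be clinically relevant". It enters the formula as 72.9 against 67.9 mmHg.
- The pilot result: "the mean mitoPO2 is 67.9 mmHg with a standard deviation of 13 mmHg". The formula, however, uses sigma = 15 mmHg.
- The formula is the square of sigma × (sum of the two z-values) / (difference in means), with no multiplier in front. It is set equal to 189. After a 10% allowance for drop-out, "the corrected sample size will be } 189 * 1.1 = 209".
- Section 5.4.1 defines what is being powered: "The primary endpoint is the change of mitoPO 2 before and after red cell transfusion".
- Section 5.1.1 says where the variance came from: "Next, using this variance, we estimated the number of patients needed to perform a reliable multicentre study".

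**The concern.** The equation that produces the sample size is not true as printed: its two sides differ by a factor of two. This is more than a slip in transcription, because that factor decides what sigma stands for. For a change measured within the same patients, a formula without the factor needs the SD of the change. A formula with it uses the SD of a single measurement and assumes that the before and after values are uncorrelated. Section 6.1 names neither quantity and gives no correlation. The SD it does report belongs to the mean level and has a different value.

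So neither the planned number nor the 90% power claim can be reproduced from the section that derives them. A well-meant correction could also do harm: someone who repairs only the arithmetic would write 95, which is far too few if 15 is the SD of the level.

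**Working it through.** **Inputs (Section 6.1):** sigma = 15 mmHg, z-values 1.96 and 1.28 (sum 3.24), difference 72.9 − 67.9 = 5 mmHg, pilot SD 13 mmHg, stated n = 189, drop-out 10%.

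**Step 1. The plan's own figure.**

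- As printed: n = (15 × 3.24/5)² = 9.72² = 94.48, so 95.
- With a factor 2: 2 × 94.48 = 188.96, which is the stated 189.
- Exact instead of rounded z-values give 94.57 and 189.13, so rounding does not explain the gap.
- Other combinations were tried: sigma 13 or 15; one- or two-sided 5%; power 80, 90 or 95%; multiplier 1, 2 or 4. Only multiplier 2 with sigma 15, two-sided 5% and 90% power gives 189.
- For the printed formula to give 189, sigma would have to be 5 × √189/3.24 = 21.2, that is 15 × √2.

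**Step 2. The pilot SD.** (13 × 3.24/5)² = 70.96, so 71; doubled, 141.93, so 142. Neither is 189.

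**Step 3. What the factor 2 implies for a before-after change.** SD of change = level SD × √(2(1 − ρ)), with ρ the before-after correlation. The protocol gives no ρ, so the values below are assumptions. With level SD 15:

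- ρ = 0: 15 × √2 = 21.21 mmHg (the factor-2 formula)
- ρ = 0.25: 15 × √1.5 = 18.37 mmHg
- ρ = 0.5: 15 × √1 = 15.00 mmHg (the same as taking 15 as the SD of the change)

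With level SD 13 and ρ = 0: 13 × √2 = 18.38 mmHg.

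**Step 4. Power for 5 mmHg.** Two-sided 5% paired t-test, noncentrality 5√n / SD of change:

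| SD of change (mmHg) | Reading | n = 189 | n = 95 |
|---|---|---|---|
| 21.21 | level SD 15, ρ = 0 | 89.7% | 62.3% |
| 18.37 | level SD 15, ρ = 0.25 | 96.1% | 74.7% |
| 15.00 | level SD 15, ρ = 0.5, or 15 is the SD of the change | 99.5% | 89.5% |

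With the pilot SD of 13 as level SD and ρ = 0, power at 189 is 96.1%. The normal approximation for the first row at n = 189 gives 90.0%, which matches the plan's target.

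**Step 5. Difference detectable with 90% power at 189** (exact z sum 3.2415): 21.21 × 3.2415/√189 = 5.00 mmHg, or 15 × 3.2415/√189 = 3.54 mmHg.

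**Step 6. Drop-out (minor).** 189 × 1.1 = 207.9, not 209. Losing 10% of 209 leaves 209 × 0.9 = 188.1 evaluable; to keep 189 needs 189/0.9 = 210. Power at 188 with SD of change 21.21 is 89.5% against 89.7% at 189.

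**The case against.** - **No reading shows a shortfall.** At 189 evaluable patients every reading above gives about 90% power or more. A clear shortfall needs an SD of change above about 21.2 mmHg, and nothing in the protocol suggests that. This stands: the defect is in the derivation and justification, not in demonstrated power.
- **A 2 may have been lost when the formula was typeset or read from the PDF.** This is possible, since one character would close the gap, though the rest of the formula reads cleanly. It would restore the arithmetic but not say what sigma is, and it would leave an unstated zero-correlation assumption behind a paired endpoint.
- **The factor 2 may simply come from the formula for two independent groups.** It may well, in which case 189 would be a number per group. Section 3.1 describes one cohort with no second group, so that origin would be a formula for the wrong design and supports the point.
- **Using 15 where the pilot gave 13 may be deliberate caution.** On 19 degrees of freedom, one-sided 75% to 80% upper confidence limits for an SD of 13 are 14.8 to 15.3. That is a reasonable motive, but the protocol does not state it. What is missing here is a sentence of explanation, not an arithmetic correction.
- **The endpoint itself varies.** The Summary names variability of mitoPO2 as the primary endpoint, and Section 5.1.1 cites a paper on sizing reliability studies. The working above takes the change in Section 5.4.1, which is also what the 5 mmHg difference in Section 6.1 describes. If another endpoint is meant, the calculation has even less connection to it.

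**Conclusion.** The point holds and must be fixed. The printed formula gives 94.5, half of the stated 189, and no other part of the protocol reconciles the two. Because sigma is undefined, the same 189 evaluable patients correspond to anything from about 90% power (15 is the SD of the level, zero correlation) to about 99.5% (15 is the SD of the change). These figures assume that the primary analysis is a two-sided 5% paired comparison of the change and that the true difference is 5 mmHg; the intermediate correlations are assumptions.

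The document cannot show whether the formula or the number is at fault. It therefore does not establish that the trial is oversized, and it gives no ground for reducing N to 95. The drop-out discrepancy is real but negligible.

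**What to change.** Rewrite the paragraph in Section 6.1 so that formula, inputs, N and power agree:

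1. State whether sigma is the SD of a single mitoPO2 measurement or of the within-patient change. Compute the SD of the change from the pilot's repeated before and after values described in Section 5.1.1.
2. State the assumed before-after correlation.
3. Give the reason for using 15 when the pilot SD is 13.
4. Then choose one of two consistent statements:
   - Print the factor: n = 2 × (15 × 3.24/5)² = 189 pairs, with level SD 15, zero correlation declared as a planning assumption, SD of change 21.2 mmHg and about 90% power.
   - If the pilot confirms an SD of change of about 15 mmHg, keep the printed formula, correct its result to 95, and restate the power at the planned 189 evaluable as about 99.5%.
5. Do not lower N to 95 unless the pilot confirms an SD of change of about 15 mmHg.
6. Minor: replace the drop-out step by 189/0.9 = 210, or say that 209 included leaves about 188 evaluable.

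The cost is one rewritten paragraph and one computation on existing pilot data. Resolving the mismatch requires no additional patients.

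### Minor arithmetic error in Protocol 6.1: 189 × 1.1 is 207.9 (208), not 209, and holding 189 after 10% drop-out takes 189 / 0.90 = 210; the gap is one patient

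*Protocol*

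**What the plan says.** Section 6.1 (Power estimate) of the protocol sets out the sample size for the multicentre cohort. The significance level is stated as "The statistical significance level will be set at the 5% level", with a multiplier of "1.96 \text{ (two tailed for } p = 0.05"). On power it says "The sample size will be calculated to achieve a statistical power of 90" per cent, with a multiplier of "1.28 \text{ (for } \beta = 0.10"). The target effect is given by "A difference in mitoPO2 of 5mmHg after red cell transfusion is deemed to be clinically relevant". The pilot result is reported as "the mean mitoPO2 is 67.9 mmHg with a standard deviation of 13 mmHg", but the sigma listed for the formula is 15 mmHg.

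The section prints a one-sample formula and equates it to 189. The last step begins "With an expected 10\% drop out rate" and ends "the corrected sample size will be } 189 * 1.1 = 209 \text{ subjects". The figure 209 appears nowhere else in the protocol.

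**The concern.** A reader who multiplies the two printed operands does not get the printed result. A drop-out rate is also ordinarily a fraction of those enrolled, so multiplying the evaluable number by 1.1 does not give that number back once 10% have been lost. The base number, the drop-out rate and the enrolment figure therefore do not fit together.

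At stake is whether the stated total can be traced to its own inputs, and whether enrolling it under the assumed loss leaves the evaluable number that the section names. The wrong inflation step would also carry over to any revised base number.

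**Working it through.** **Inputs, all from Protocol 6.1:** base n = 189; drop-out 10%; stated total 209; multipliers 1.96 and 1.28; difference 72.9 − 67.9 = 5 mmHg; sigma 15 mmHg.

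**1. The plan's own product**
- 189 × 1.1 = 207.9, rounded up to 208. The printed 209 is not reproduced.
- 190 × 1.1 = 209 exactly, but 190 is not the printed base.

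**2. Can rounding explain 209?**
- The value 189 arises from 2 × (15 × (1.96 + 1.28) / 5)² = 2 × 9.72² = 188.96. The factor of 2 is not in the printed formula.
- With the printed multipliers: 188.96 × 1.1 = 207.86, rounded up to 208.
- With unrounded normal quantiles: n = 189.13, and 189.13 × 1.1 = 208.05, which rounds up to 209. But 189.13 itself rounds up to 190, not 189.
- So 209 can be reached by rounding only with multipliers other than the printed ones, and rounding up consistently would then make the base 190.

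**3. The operation.** If a fraction d of those enrolled is lost, enrolment N leaves N(1 − d), so N = n / (1 − d).
- Enrolment needed to keep 189: 189 / 0.90 = 210.
- Enrolling 209 leaves 209 × 0.90 = 188.1.
- Enrolling 208 leaves 208 × 0.90 = 187.2.

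**4. Effect on power, on the calculation that yields 189.** Power = Φ(5/15 × √(n/2) − 1.96).

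| Evaluable n | Power |
|---|---|
| 187 | 89.67% |
| 188 | 89.83% |
| 189 | 89.98% |

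The difference between 188 and 189 is 0.15 points, or about 0.2 points.

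**5. The base number, by the formula as printed**
- (15 × 3.24 / 5)² = 94.48, rounded up to 95, not 189.
- With the pilot SD of 13: (13 × 3.24 / 5)² = 70.96, rounded up to 71.
- Power under the printed one-sample form, Φ(5/15 × √n − 1.96), is 99.5% at 188 and 99.6% at 189.
- If 95 were the requirement, drop-out inflation gives 95 / 0.90 = 105.6, so 106; multiplying gives 95 × 1.1 = 104.5, so 105. The choice of operation still moves the total by one.

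**The case against.** The strongest case on the other side has four parts.

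- **The gap is trivial and looks like rounding.** The printed 209 lies one away from both 208 and 210, and an unrounded 189.13 leads to it. The size of the gap is not in dispute. The rounding explanation is an inference: it needs multipliers that the section does not print, and it unsettles the printed 189. It does not make the equation true.
- **The drop-out rate is only a planning guess.** At 9.5% loss, 209 × 0.905 = 189.1 would remain. This stands, and it is a good reason not to speak of a missed requirement. It does not make multiplication by 1.1 the right step for a stated 10%.
- **Drop-out need not mean loss from the analysis.** Sections 8.2 and 8.3 keep data collected up to the point at which a participant declines to continue. This stands in part. Section 8.2 also removes the data when consent is retracted after participation, and section 10 (g) excludes subjects for whom written consent is never obtained.
- **The base of 189 is itself unsupported.** The printed formula gives 95. On that figure 209 would be ample, tolerating a loss of 1 − 95/209, or about 54%. This stands, and it is why replacing the line by 210 alone would only polish an unsupported number.

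A reader might infer that the study is under-enrolled, or that recruitment and reporting are tied to a wrong target. The documents do not support either reading. The shortfall exists only if 189 is the true requirement, and it is then one patient. No other section links recruitment, stopping or reporting to 209.

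**Conclusion.** The point holds as a minor arithmetic correction. The printed product is wrong (207.9, so 208, not 209), and the step that preserves 189 under 10% loss is division by 0.90, giving 210. The size is one evaluable patient and about 0.2 points of power.

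This rests on two assumptions: that the 10% is a fraction of those enrolled and lost to the analysis, and that 189 is taken as printed for the purpose of the check. The second is doubtful. The value 189 needs an unprinted factor of 2, which belongs to a comparison of two independent groups, whereas section 5.4.1 defines the primary endpoint as a before-to-after change in one cohort. The SD of the within-patient change is not given, so the correct base number cannot be settled from the protocol.

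**What to change.** Restate the last line of section 6.1 so that its figures agree, without raising enrolment: 209 enrolled, 10% expected drop-out, about 188 evaluable, with 89.8% power on the calculation that yields 189. State the drop-out step as division by (1 − 0.10).

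Make this change together with reconciling the base number: state which formula is used, and explain why sigma is 15 when the pilot SD is 13. Then divide whatever evaluable number results by 0.90. For example, a base of 95 would become 106.

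The cost of the drop-out correction is one line of protocol text and no additional subjects.

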### 6.2 Statistical methods to be employed

Absolute differences and 95% confidence intervals will be calculated. In addition to the univariate comparisons we will also calculate the differences for each of the parameters independent of the other parameters using multivariate models. In addition, we will perform similar analyses in subgroups of Hb and reason of admission (classified by APACHE IV) to assess whether the observed effect of transfusion on the parameters differs between the groups. We will also examine whether the decrease of the mitoPO2 precedes changes of other measures of oxygenation.

For the dichotomous outcomes logistic regression will be applied. For time-to event outcomes the univariable analysis will be performed using the Kaplan-Meier method, the multivariable analyses the Cox proportional hazard model. To determine the discriminative power of the model, the ROC curve with the c-statistic.  $P < 0.05$  will be considered statistically significant for the primary outcome measure. The statistical analysis will be conducted using the SPSS (Statistical Package for the Social Sciences) statistical package, release 23.0 (SPSS Inc., Chicago, IL) and STATA.

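### Repeating the before/after analysis within Hb and admission subgroups neither estimates nor tests whether the transfusion effect differs between them

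*Protocol*

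**What the plan says.** Protocol section 6.2 begins with the basic analysis: "Absolute differences and 95% confidence intervals will be calculated". It adds multivariate models and then says "we will perform similar analyses in subgroups of Hb and reason of admission (classified by APACHE IV", with the purpose "to assess whether the observed effect of transfusion on the parameters differs between the groups". Section 5.1.1, straight after describing the comparison of values before and after transfusion, gives the same plan and the same purpose: "to assess whether the observed effect of red cell transfusion on the parameters differs between the groups".

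So a method (repetition within subgroups) and a question (does the effect differ between subgroups) are both stated, in two places. The protocol contains no interaction term, heterogeneity test or between-subgroup contrast. It gives no Hb cut-points, number of admission categories or subgroup sizes. In section 6.2 the P < 0.05 criterion is attached to the primary outcome measure only.

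**The concern.** The stated method does not answer the stated question. A within-subgroup analysis asks whether the change in that subgroup is zero. Whether two changes differ is another quantity with its own standard error, and it has to be estimated directly. Someone following the text would hold a set of subgroup estimates and would have to choose an informal way of comparing them. The two obvious ways fail in opposite directions:

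- Noting which subgroups are significant can suggest a difference when the effects are equal.
- Looking for non-overlapping confidence intervals can hide a difference that exists.

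The results are meant to inform the design of a later study (section 1). An apparent Hb-specific response, or an apparent absence of one, could carry over into that design.

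**Working it through.** **Inputs from the protocol (section 6.1).** Effect 5 mmHg: "A difference in mitoPO2 of 5mmHg after red cell transfusion is deemed to be clinically relevant". Two-sided alpha 0.05: "The statistical significance level will be set at the 5% level". Planned power 90%. Pilot SD 13 mmHg; σ = 15 mmHg in the calculation. Sample size 189, or 209 with drop-out.

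**The plan's own figure.** (15 × (1.96 + 1.28) / 5)² = 94.5, whereas 2 × 94.48 = 188.96, which rounds to 189. The stated 189 thus matches twice the printed formula. That is a separate matter. Its relevance here is that 189 paired patients give 90% power for 5 mmHg when the SD of the change is 15 × √2 = 21.2. Evaluable patients after 10% drop-out: 209 × 0.9 = 188.

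**Assumptions (not in the protocol).** Two, three or four equal subgroups (94, 63 or 47 patients each). SD of the within-patient change = σ√(2(1 − r)), where r is the before/after correlation:
- σ = 15: r = 0 gives 21.2; r = 0.5 gives 15.
- σ = 13: r = 0.5 gives 13; r = 0.7 gives about 10; r = 0.8 gives 8.2.

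**Reading 1: compare significance.** With the same true effect in all k subgroups and power p in each (paired t-test, noncentral t), the chance that some but not all are significant is 1 − pᵏ − (1 − p)ᵏ. Example at SD 15, two groups: p = 0.892, so 1 − 0.796 − 0.012 = 0.192.

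| SD of change | Two of 94: p, discordant | Three of 63 | Four of 47 |
|---|---|---|---|
| 8.2 | >0.99, about 0% | 0.998, 0.8% | 0.984, 6% |
| 10 | 0.998, 0.5% | 0.974, 7.5% | 0.919, 29% |
| 13 | 0.958, 8% | 0.852, 38% | 0.733, 71% |
| 15 | 0.892, 19% | 0.740, 58% | 0.609, 84% |
| 21.2 | 0.619, 47% | 0.453, 74% | 0.353, 81% |

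With four groups the rate peaks between the last two rows, at about 87% for an SD of 18. Rates are per parameter and per factor.

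**Reading 2: compare 95% confidence intervals by overlap.** Two equal groups fail to overlap when the estimates differ by more than 2 × 1.96 × SE. The SE of their difference is √2 × SE, so this requires |Z| > 1.96 × √2 = 2.77. With equal true effects that happens in about 0.6% of cases; some pair fails to overlap in about 1.5% with three groups and 2.9% with four. The cost is sensitivity. At SD 15, SE = 15/√94 = 1.547. A real 5 mmHg difference gives (5 − 6.065) / 2.188 = −0.49, so the intervals separate in about 31% of cases.

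**Direct estimate (interaction).** In simulation at SD 15 (100,000 runs, 189 patients), an F-test of subgroup by change gave a false-difference rate of 4.9% for two groups, 4.9% for three and 5.0% for four. Its power for a true 5 mmHg difference between two groups of 94, by normal approximation: SD 15, SE = 15 × √(2/94) = 2.19, power about 63%; SD 21, SE = 3.06, power about 37%. For 90% power at SD 15, about 190 patients per subgroup are needed.

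**The case against.** A reader might infer that the protocol will declare a difference whenever one subgroup is significant and another is not, and hence that it will often report differences that do not exist. The text does not say so. It plans differences with 95% confidence intervals and ties P < 0.05 to the primary outcome, and comparing intervals by overlap is conservative. The discordance rates therefore depend on a decision rule that the protocol does not state. They also depend on an SD of change and on subgroup numbers that it does not give; with two groups and an SD of 10 or below the rate is close to zero. This part of the objection stands.

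A reader might also infer that effect modification by Hb is a central claim. It is not among the objectives in section 2.2 or the outcomes in section 5.4. Tailoring transfusion is the aim of the wider project (section 2.1), and section 1 says the results cannot be translated immediately into practice. This stands too.

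The remaining objection is that a formal comparison belongs in the analysis plan mentioned in section 9.6, which is not at hand. Cut-points and model details do belong there. But the protocol is not silent: it assigns subgroup repetition to a between-group question. An analysis plan that followed it literally would keep the mismatch; one that added a contrast would cure it.

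Entering Hb as a continuous variable is a preference. It brings a linearity assumption, and the information lost by grouping cannot be sized without cut-points.

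**Conclusion.** The point holds as a mismatch between method and purpose in sections 5.1.1 and 6.2: within-subgroup estimates neither test nor estimate a between-subgroup difference, and no rule for comparing them is given. It does not hold as a prediction that false differences will often be reported.

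If significance were compared, equal true effects of 5 mmHg would give discordant results in about 8–47% of cases with two groups, 38–74% with three and 71–84% with four at the tabulated SDs of change from 13 to 21 mmHg, with a peak of about 87% for four groups near an SD of 18. If intervals were compared by overlap, false differences would be rare (about 0.6% with two groups), but a real 5 mmHg difference would show in only about 31% of cases at SD 15, against about 63% with a direct test. All these figures assume equal subgroups and about 188 evaluable patients.

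These are supporting analyses, so the primary result is not affected. The correction is worthwhile because it is cheap and because the question asked is about a difference between groups.

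**What to change.** In sections 5.1.1 and 6.2, replace the subgroup-by-subgroup assessment with one whole-cohort model of the before/after change containing two sets of terms:

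- period by baseline Hb, preferably continuous, with linearity checked;
- period by admission category.

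Report the interaction estimates with 95% confidence intervals as the answer to whether the effect differs. Show the changes within subgroups as description only. Label these analyses exploratory and state the limited power given above, so that an interval including zero is not read as evidence of equal effects.

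The cost is a rewording in two sections and the interaction terms for each modifier: one for continuous Hb, and one fewer than the number of categories for admission reason. No new data, measurements or patients are needed.

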### 5.4.2 Secondary outcomes

Secondary study outcomes include:

- Value of mitoPO2 measurements in predicting (ischemic) organ damage. The following parameters for organ damage (that are routinely collected) will be assessed: lung (pO2/FiO2 ratio), heart (troponin, CK, an ECG, CI), renal (creatinine, urine production, glomerular filtration rate, RIFLE classification), brain (delirium, RASS) and SOFA score. More details about the timing of these parameters are given in appendix 2.
- Microcirculatory value of mitoPO2
- Duration of mechanical ventilation
- Need for renal replacements therapy
- Length of ICU stay
- Length of stay in hospital
- Hospital mortality
- ICU mortality
- 90-day mortality
- Assessment the safety of mitoPO2 measurements
  - Delay of transfusion because of mitoPO2 measurements
  - Adverse and serious adverse events of the mitoPO2 measurements

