### 7.4 Serious adverse events (SAEs)

A serious adverse event is any untoward medical occurrence or effect that

- results in death;
- is life threatening (at the time of the event);

- 
- requires hospitalisation or prolongation of existing inpatients' hospitalisation;
  - results in persistent or significant disability or incapacity;
  - Any other important medical event that did not result in any of the outcomes listed above due to medical or surgical intervention but could have, based upon appropriate judgement by the investigator.

An elective hospital admission will not be considered as a serious adverse event.

The investigator will report all SAEs to the sponsor without undue delay after obtaining knowledge of the events. Patients on the ICU are critically ill and therefore more prone to SAEs. ICU mortality in the Netherlands is approximately 8.4%. Thirty-five percent of the patients are in need for vasopressor therapy, and 46% of the patients are mechanically ventilated. Furthermore, the National Intensive Care Evaluation Report of 2015 reports that the mean ICU admittance duration is 3 days with a mean in hospital admittance duration of 13 days. Around 80% of the total ICU patients have a low APACHE IV score, and therefore a mortality chance of less than 30%. Thus, SAEs in relation to underlying disease and expected SAEs during the ICU course will not be reported.

The coordinating investigator will report the SAEs through the web portal *ToetsingOnline* to the accredited METC that approved the protocol, within 7 days of first knowledge for SAEs that result in death or are life threatening followed by a period of maximum of 8 days to complete the initial preliminary report. All other SAEs will be reported within a period of maximum 15 days after the sponsor has first knowledge of the serious adverse events.

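### Kaplan-Meier and Cox are the only time-to-event methods named, but death competes with discharge and extubation in the three duration outcomes: a cheap improvement to section 6.2

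*Protocol*

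**What the plan says.** Protocol section 6.2 assigns methods by type of outcome. Binary outcomes come first: "For the dichotomous outcomes logistic regression will be applied". The next sentence reads: "For time-to event outcomes the univariable analysis will be performed using the Kaplan-Meier method, the multivariable analyses the Cox proportional hazard model". The section does not say which outcome belongs to which type.

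Section 5.4.2 lists the secondary outcomes. Three are durations: "Duration of mechanical ventilation", "Length of ICU stay" and "Length of stay in hospital". Three are worded as occurrences: "Hospital mortality", "ICU mortality" and the need for renal replacement. Mortality at 90 days has a fixed horizon and counts death from any cause.

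Nowhere does the protocol mention competing events or cumulative incidence. It also does not say whether a death is censored or counted as the end of a stay or of ventilation. Section 7.4 gives background figures for Dutch ICUs in general: "ICU mortality in the Netherlands is approximately 8.4" percent, with a mean ICU stay of 3 days.

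**The concern.** The three durations are not binary, so within section 6.2 their natural place is under Kaplan-Meier and Cox. A patient who dies in the ICU can no longer be discharged alive, and a patient who dies on the ventilator can no longer be extubated. Kaplan-Meier with such patients censored treats them as if they could still reach the event later, so the estimated proportion discharged or extubated is too high.

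This matters for what the study wants to learn. Objective 3 in section 2.2 relates mitoPO2 to organ function, including ventilation time, and the introduction hypothesises that mitoPO2 predicts organ dysfunction early. If low mitoPO2 goes together with death, the handling of death becomes part of the estimated association with stay and ventilation.

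**Working it through.** The protocol gives no figure of its own here, so there is nothing to reproduce. The check is an illustration for ICU stay.

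**Inputs.** Mean ICU stay L = 3 days and share dying in the ICU m = 8.4%, both from section 7.4. Both are national figures for all ICU patients. The study enrols anaemic patients with a planned transfusion and excludes those expected to stay under 24 hours. Values of m = 20% and 30% are assumptions that show the range.

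**Model.** Constant hazards with a total exit rate of 1/L per day. The hazard of death is m/L and that of live discharge is (1 − m)/L.

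- Actual probability of live discharge by day t (cumulative incidence): (1 − m) × (1 − exp(−t/L)).
- One minus Kaplan-Meier with deaths censored: 1 − exp(−(1 − m) × t/L).

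**Day 7, m = 8.4%.** Cumulative incidence: 0.916 × (1 − exp(−7/3)) = 0.916 × 0.903 = 0.827. Kaplan-Meier: 1 − exp(−0.916 × 7/3) = 1 − exp(−2.137) = 0.882. The gap is 5.5 percentage points.

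| m | Day | Cumulative incidence | 1 − Kaplan-Meier | Gap (points) |
|---|---|---|---|---|
| 8.4% | 3 | 57.9% | 60.0% | 2.1 |
| 8.4% | 7 | 82.7% | 88.2% | 5.5 |
| 8.4% | 28 | 91.6% | about 100% | 8.4 |
| 20% (assumed) | 7 | 72.2% | 84.5% | 12.3 |
| 20% (assumed) | 28 | 80.0% | 99.9% | 19.9 |
| 30% (assumed) | 7 | 63.2% | 80.5% | 17.3 |
| 30% (assumed) | 28 | 70.0% | 99.9% | 29.9 |

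**The alternative: death counts as the end of the stay.** Kaplan-Meier is then unbiased for leaving the ICU by any route: 1 − exp(−7/3) = 90.3% by day 7. At m = 8.4% this is 82.7% discharged plus 0.084 × 0.903 = 7.6% dead, two opposite results added together.

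**What one Cox model can and cannot show.** Take two hypothetical groups with the same discharge hazard, 0.916/3 = 0.3053 per day. Let the death hazard be 0.084/3 = 0.028 in one and twice that, 0.056, in the other.

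- The cause-specific hazard ratio for discharge is 1, which is correct.
- The proportion eventually discharged alive is 0.3053/0.3333 = 91.6% in the first group and 0.3053/0.3613 = 84.5% in the second.
- The mean stay, deaths included, is 1/0.3333 = 3.0 days and 1/0.3613 = 2.8 days. The group with more deaths has the shorter stay.

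The ratio of 1 shows neither difference. The companion model for death is needed to see where they come from.

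Ventilation time and hospital stay have the same structure. They cannot be sized here, because the protocol gives no share of patients dying on the ventilator or in hospital.

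**The case against.** The strongest objection is that the protocol never says deaths will be censored, nor that the durations will be analysed by Kaplan-Meier at all. They could be compared as days under the absolute differences with which section 6.2 opens. The assignment of outcomes to methods and the censoring rules are commonly left to an analysis plan, which section 9.6 foresees and which is not shown here. Part of this stands: the bias is conditional on censoring, and the outcomes are secondary. It does not remove the point. Section 6.2 does name its time-to-event methods, a more suitable standard set exists for the three durations, and a comparison of days gives no rule for death either.

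A reader might go further and infer that every outcome except 90-day mortality is affected, including ICU mortality, hospital mortality and renal replacement. For ICU death the distortion would look dramatic: with discharges censored at m = 8.4%, one minus Kaplan-Meier at day 28 is 1 − exp(−0.028 × 28) = 54.3%, against an actual 8.4%. The protocol does not support that reading. These three outcomes are worded as yes/no, and the sentence just before the Kaplan-Meier sentence sends such outcomes to logistic regression, where this distortion does not arise.

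A reader might also infer that the Cox model is wrong. It is not. With deaths censored it validly estimates a cause-specific hazard ratio, a usable measure for the stated aim of describing association. The limit is on its interpretation when reported alone.

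**Conclusion.** The point holds for the three durations only. If deaths are censored, Kaplan-Meier would overstate live ICU discharge by about 5 to 6 points at day 7 and about 8 points at day 28 on the protocol's own background figures. At an assumed mortality of 20% to 30%, the overstatement at day 7 would be about 12 to 17 points. If death ends the stay, the curve is unbiased for any exit, but early deaths pass as short stays.

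The sizes rest on constant hazards and on national all-ICU figures. Higher mortality in this cohort is plausible, but the documents do not give it. This is a cheap improvement of low to moderate priority; it does not touch the primary endpoint.

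**What to change.** In section 6.2:

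- Describe time on the ventilator, ICU stay and hospital stay by cumulative incidence (Aalen-Johansen), with death as the competing event.
- Model each with two cause-specific Cox models, one for extubation or live discharge and one for death, and report both together.
- Keep Kaplan-Meier and Cox for 90-day mortality.
- Confirm that ICU mortality, hospital mortality and need for renal replacement are binary and go to logistic regression, as the section already implies.

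The cost is a few sentences and a little analysis code. STATA is already named in section 6.2, and sections 5.3.2 and 5.3.3 already provide for collecting ventilation time, stay and mortality. The downside is two hazard models to report per duration instead of one.
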